3.3 Efficacy

Improvement in renal function is the goal of therapy for HRS-AKI; improvement in renal function is associated with improvement in clinical outcomes and improved prognosis, with or without liver transplantation. HRS reversal is a widely accepted, clinically meaningful response to treatment for HRS Type 1, as apparent inexorable, rapid progression of renal failure is arrested and normal renal function in the setting of decompensated liver disease is restored. The primary endpoint of HRS reversal (1 serum creatinine [SCr] value of ≤ 1.5 mg/dL) is the standard endpoint utilized in the literature and HRS treatment guidelines (Arroyo, 1996; Salerno, 2007; Angeli, 2015). Both terlipressin bolus and continuous infusion have been shown to be effective

in the treatment of HRS Type 1, with fewer adverse events occurring in the cohort receiving continuous infusion. (Cavallin, 2016).

3.4 Safety

The safety characteristics of terlipressin is captured in the literature and post-marketing data from the World Health Organization (WHO) database. In general, terlipressin has a well-established safety profile in the treatment of patients with HRS Type 1. The safety risks are predictable and recognizable. The adverse drug reactions can be readily managed and reversed by terlipressin dose reduction or interruption in hospital-care settings. Continuous infusion of terlipressin may be more tolerable than bolus injection (Cavallin, 2016).

3.5 Retrospective Control Group: M&O Treated Subjects

3.5.1 Midodrine and Octreotide

Midodrine is an oral alpha-receptor agonist that binds to peripheral alpha-receptors on both arterioles and veins, leading to an increase in blood pressure (Cruz, 2000). Midodrine is a prodrug; it is transformed into the active metabolite de-glymidodrine, a compound similar in structure to norepinephrine (Cruz, 2000). Midodrine was approved for use in the United States for treatment of orthostatic hypotension in 1996. Octreotide is somatostatin analogue that binds to somatostatin receptors and mimics the physiologic effects of somatostatin including inhibition of various hormones, some of which lead to vasodilation, thus octreotide can cause arteriolar vasoconstriction leading to increases in blood pressure (Gold Standard). Octreotide can be administered via intravenous or subcutaneous routes and was approved for use in the United States in 1988 for treatment of certain neuroendocrine tumors.

3.5.2 M&O Off-Label Use

The combination of midodrine/octreotide (M&O), in conjunction with albumin, has been used “off-label” in the United States for treatment of HRS Type 1 for years. Small studies, mostly single center, have demonstrated favorable outcomes for M&O in treatment of HRS Type 1 (Angeli, 1999; Wong, 2004; Esrailian, 2007). The use of M&O plus albumin is recommended in the 2012 AASLD guidelines for the treatment of HRS Type 1 (Runyon, 2013), particularly in light of the fact that terlipressin was not available in the United States at the time of publication. However, the largest multi-centered study comparing terlipressin to M&O undertaken by the Italian Association for the Study of the Liver Study Group on Hepatorenal Syndrome, was stopped early due to the considerable differences in HRS reversal between terlipressin and M&O (55.5 vs 4.8%, p<0.001) (Cavallin, 2015).

Midodrine/Octreotide use in patients on the liver transplant wait list with HRS Type 1

Increasing the duration of time in which a patient with decompensated cirrhosis experiences renal dysfunction decreases the likelihood of renal recovery after liver transplant (Campbell, 2005). Wong et al retrospectively evaluated patients that had experienced HRS Type 1 without reversal prior to liver transplant at University of Toronto between 2001 to 2010 (n=62); M&O was used as treatment of HRS Type 1 in the majority of these patients (Wong, 2015). While none of the patients in the cohort had HRS reversal, 76% were free from dialysis 30 days after liver transplant and had a serum creatinine ≤ 1.5 mg/dL (Wong, 2015). The duration of HRS type 1 and the number of dialysis days prior to liver transplant were highly predictive of post-transplant renal function (Wong, 2015). Additionally, those patients that were not dialysis-free 30 days post-transplant with serum creatinine ≤ 1.5 mg/dL had higher mortality rates (Wong, 2015). This data suggests that even if HRS reversal is not possible, that limiting the dialysis days and length of HRS type 1 can lead improve renal outcomes post-transplant.

4 Study Rationale

The purpose of this open labeled study is to assess safety/efficacy for continuous terlipressin infusion in liver transplant-eligible adult subjects with Hepatorenal syndrome- Acute Kidney Injury (HRS-AKI).

5 Safety and Efficacy Assessments

5.1 Efficacy Variables

The efficacy variables are summarized below, and further details are provided in Section 13.

Primary Efficacy Assessment:

Improvement of renal function (SCr) from Day 1 through end of treatment, repeated measure analysis. SCr will be collected daily, from Day 1 through end of treatment. Baseline SCr will also be entered.

Secondary Efficacy Endpoints:

- Improvement of renal function (SCr) from Day 1 through end of treatment, repeated measure analysis as compared to the Retrospective Control Group.
- For the Prospective Terlipressin Group alone and also in comparison to the Retrospective Control Group:
 - Incidence of dialysis by Day 30 and Day 90 of follow up.

Collaborative Research Study, Version 4: 06/29/21
To Treat HRS-AKI Patients with Continuous Terlipressin Infusion

- Survival by Day 30 and Day 90 follow up.
- Transplant by Day 30 and Day 90 follow up.
- Serum creatinine at Day 30 and Day 90 follow up
- Serum creatinine and incidence of dialysis at Day 30, Day 90, Day 180, and Day 365 after liver transplantation and those alive without transplantation (transplant eligible and ineligible patients)
- Incidence of kidney transplant within one year after liver transplant.
- Descriptive analysis of number simultaneous liver kidney transplants and episodes of graft rejection at Day 90 and Day 365 after liver transplant.

Safety:

Safety review and assessments will be made only for the Prospective Terlipressin Group and will include the following:

- Serious adverse events up to 30 days after end of treatment.

6 Investigational Plan

6.1 Overall Study Design and Plan: Description

Prospective Terlipressin Group

This is a collaborative open-label, multicenter study of terlipressin infusion following an initial bolus dose of 0.5mg. Written informed consent will be obtained by the investigator, sub-investigator, or qualified designee from the subject or legally authorized representative (LAR) prior to the subject enrollment into the study. Approximately 50 subjects are planned to be enrolled at 5-10 sites in the US. Subjects will receive up to 14 days of terlipressin treatment.

Retrospective Control Group

This study will also seek clinical data from a Retrospective Control Group of patients who would have met inclusion/exclusion criteria detailed below and received at least 48 hours of treatment with Midodrine and Octreotide (M&O), albumin, or other vasopressor used for the treatment of HRS-AKI. Retrospective cases collected from each site should include eligible patients starting from prior to site IRB approval for this protocol and going back to January 2015. Subjects enrolled in a blinded clinical trial in this time period are excluded.

7 Study Population

7.1 Population Rationale

The study population consists of adult subjects with cirrhosis, ascites, and a diagnosis of HRS AKI based on based on the 2015 revised International Ascites Club (IAC) diagnostic criteria.

7.2 Number of Subjects to be Studied

Prospective Terlipressin Group - approximately 50 Terlipressin treated subjects. Retrospective Control Group - approximately 15-25 subjects per clinical site that were treated for HRS-AKI according to center's standard-of-care (Midodrine/Octreotide (M&O), albumin, or other vasopressor) that would have met the inclusion/exclusion criteria below as well as having critical clinical data points to enable a comparison of the Prospective and Retrospective groups. Retrospective cases collected from each site should include eligible patients starting from prior to site IRB approval for this protocol and going back to January 2015. Subjects enrolled in a blinded clinical trial in this time period are excluded.

7.3 Inclusion/Exclusion Criteria

Adult subjects with a diagnosis of HRS-AKI based on 2015 revised International Ascites Club (IAC) diagnostic criteria will be considered for enrollment. There are two groups: 1. listed for liver transplant or liver transplant eligible with anticipation of being placed on the liver transplant wait list; 2. Ineligible for liver transplant

Inclusion Criteria: Subjects must meet all of the following inclusion criteria to be eligible for enrollment:

1. Written informed consent by subject or legally authorized representative.
2. At least 18 years of age.
3. Cirrhosis and ascites.
4. No sustained improvement in renal function (less than 20% decrease in SCr) at least 48 hours after diuretic withdrawal and after plasma volume expansion with albumin (given daily for two days - 48 hours minimum from 1st dose). If SCr improves by $\geq 20\%$ but plateaus ($\leq 10\%$ fluctuation in sCr) and remains above 1.5 mg/dl for \geq another 48 hrs and there are no features of acute tubular necrosis.

Collaborative Research Study, Version 4: 06/29/21
To Treat HRS-AKI Patients with Continuous Terlipressin Infusion

5. Increase in SCr by at least ≥ 0.3 mg/dl OR 1.5-2 fold above baseline (AKI stage 1 and above), to a SCr of ≥ 1.5 mg/dl at the time of initiating treatment. Baseline SCr is defined as the most recent, lowest SCr within last 6 months before date of current admission.
6. A.) On liver transplant wait list or liver transplant eligible with anticipation of being placed on the liver transplant wait list. B.) Patients not on the transplant waitlist or transplant eligible are also eligible for the trial (maximum 25 subjects)

Exclusion Criteria: If any of the following exclusion criteria are met, the subject will not be enrolled:

1. Serum creatinine level greater than 5.0 mg/dL. Subjects with value greater than 5.0 mg/dL may be enrolled with Sponsor prior approval.
2. MELD score ≥ 35
3. Acute on Chronic Liver Failure (ACLF) grade 3 (according to the CLIF Consortium grading system).
4. Uncontrolled sepsis and/or uncontrolled bacterial infection (e.g., persisting bacteremia, persisting ascitic fluid leukocytosis, fever, increasing leukocytosis with vasomotor instability).
5. Shock.
6. Current or recent (within 4 weeks) treatment with or exposure to nephrotoxic agents: e.g., aminoglycosides, amphotericin, cyclosporine A, cisplatin, nonsteroidal anti-inflammatory drugs (NSAIDs: e.g., ibuprofen, naproxen, diclofenac), significant exposure to radiographic contrast agents (large doses or multiple injections of iodinated contrast media; e.g., during coronary or abdominal angiogram).
7. Estimated life expectancy of less than 7 days.
8. Advanced Hepatocellular Carcinoma (HCC) with expected survival of < 6 months.
9. Superimposed acute liver injury due to drugs (e.g., acetaminophen), dietary supplements, herbal preparations, viral hepatitis, or toxins (e.g., *Amanita* toxin with mushroom poisoning carbon tetrachloride), with the exception of acute alcoholic hepatitis.
10. Evidence of obstructive uropathy or parenchymal renal disease. Renal ultrasound or other imaging not required but should be taken if suspicious.

Collaborative Research Study, Version 4: 06/29/21
To Treat HRS-AKI Patients with Continuous Terlipressin Infusion

11. Tubular epithelial casts, heme granular casts (range of 1-3 granular casts acceptable), hematuria or microhematuria on urinalysis that is indicative of acute tubular necrosis and/or intrinsic renal disease.
12. Subjects known to be pregnant; all women of child-bearing age and potential must have a negative pregnancy test.
13. Severe cardiovascular disease, including, but not limited to, unstable angina, pulmonary edema, congestive heart failure, or persisting symptomatic peripheral vascular disease, myocardial infarction or stable chronic angina within the past 12 months, or any other cardiovascular disease judged by the investigator to be severe and creates a risk to subject with concurrent terlipressin use.
14. Current or recent (within 4 weeks) renal replacement therapy (RRT) or anticipation of RRT within 3 days on enrollment.
15. Participation in other clinical research involving investigational medicinal products within 30 days of starting study drug that would adversely affect participation in this or the current trial.
16. Transjugular intrahepatic portosystemic shunt (TIPS) within 30 days of starting study drug.
17. For the Prospective Group: All vasopressors must be stopped prior to treatment with terlipressin. Use of vasopressors (eg, norepinephrine, epinephrine or vasopressin dopamine or other vasopressors) of ≥ 3 consecutive days within the prior 14-day screening period are excluded. Patients receiving a vasopressor other than midodrine within 24 hours of qualifying SCr are excluded, i.e, a 24-h washout is required prior to enrollment.
Note: Patients receiving midodrine and octreotide may be enrolled. Midodrine and octreotide treatment must be stopped prior to enrollment.
18. Known allergy or sensitivity to terlipressin.

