1 SYNOPSIS

(synopsis to follow)

SYNOPSIS
Name of Sponsor/Company: University of Pennsylvania
Name of Investigational Product: Terlipressin
Name of Active Ingredient: Terlipressin
Title of Study: A Multi-Center, Open Label, Collaborative Research Study to Treat HRS-AKI Patients with Continuous Terlipressin Infusion
Study Centers: Approximately 5-10 sites in the United States of America
Phase of Development: Phase 3
Objectives: Primary: To assess safety/efficacy for continuous terlipressin infusion in adult subjects with Hepatorenal syndrome- Acute Kidney Injury (HRS-AKI) who are in one of two groups: 
1. On the liver transplant wait list or liver transplant eligible with anticipation of being placed on the liver transplant wait list2. Not eligible for liver transplant (limited to 25 patients)
Methodology: Prospective Terlipressin Group - Patients to be treated with open label terlipressin by infusion following an initial bolus dose of 0.5mg. Retrospective Control Group – Historical patients who would have met inclusion/exclusion criteria detailed below and received at least 48 hours of treatment for HRS-AKI according to center's standard-of-care (Midodrine/Octreotide (M&O), albumin, or other vasopressor)
Number of Subjects (Planned): Prospective Terlipressin Group - approximately 50 terlipressin treated subjects Retrospective Control Group - approximately 15-25 subjects per clinical site that were treated for HRS-AKI, that would have met the inclusion/exclusion criteria below as well as having critical clinical data points to enable a comparison of the Prospective and Retrospective groups. Retrospective cases collected from each site should include eligible patients starting from prior to site IRB approval for this protocol and going back

Collaborative Research Study, Version 4: 06/29/21
To Treat HRS-AKI Patients with Continuous Terlipressin Infusion

to January 2015. Subjects enrolled in a blinded clinical trial in this time period are excluded.

Diagnosis and Main Inclusion/Exclusion Criteria:

Adult subjects that are listed for liver transplant or liver transplant eligible with anticipation of being placed on the liver transplant wait list and have a diagnosis of HRS-AKI based on 2015 revised International Ascites Club (IAC) diagnostic criteria.

Inclusion Criteria:

1. Written informed consent by subject or legally authorized representative.
2. At least 18 years of age.

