13.2 Secondary Efficacy Variables

- Improvement of renal function (SCr) from Day 1 through end of treatment, repeated measure analysis as compared to the Retrospective Control Group.
- For the Prospective Terlipressin Group alone and also in comparison to the Retrospective Control Group:
 - Incidence of dialysis by Day 30 and Day 90 of follow up.
 - Survival by Day 30 and Day 90 follow up.
 - Transplant by Day 30 and Day 90 follow up.
 - Serum creatinine at Day 30 and Day 90 follow up
 - Serum creatinine and incidence of dialysis at Day 30, Day 90, Day 180, and Day 365 after liver transplantation
 - Incidence of kidney transplant within one year after liver transplant
 - Descriptive analysis of number simultaneous liver kidney transplants and episodes of graft rejection at Day 90 and Day 365 after liver transplant

14 Serious Adverse Events

Only Serious Adverse Events will be collected for this study for the prospective group only. Safety review and assessments will be made only for the Prospective Terlipressin Group from time of first dose through 30 days after end of treatment. SAEs are collected from the start of study drug until 30 days after study drug was discontinued. Non-serious Adverse Events are not required to be collected for this study.

The investigator will record the nature, causality, severity, treatment, and outcome of the SAE, and will determine whether there is a “reasonable probability” that the study drug treatment caused the event.

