15.2 Secondary Analyses

A number of secondary outcomes will be examined for the study cohort. These outcomes include the incidence of dialysis, mortality, and liver transplantation at day 30 and 90. The

incidence of kidney transplant within one year of liver transplant will also be determined. Additionally, descriptive comparisons of SCr will be undertaken at day 30 and 90 of follow up and at 4 time points after receipt of liver transplantation (day 30, 90, 180 and 365) and also at similar time points for those patients who were transplant ineligible or did not undergo a transplant. Incidence will be calculated as the number of new events during the observation period divided by the total persons at risk. All statistical analyses will be conducted using Stata version 15.1 statistical software (StataCorp, College Park, TX). Statistical significance will be declared for a two-sided hypothesis test if the *P* value was <0.05.

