15.3 Sample Size Considerations

A formal sample size calculation is not applicable for the proposed study. However, at least 50 subjects across more than 5-10 institutions may receive terlipressin treatment during the course of the intervention portion of the study. For the comparison of the terlipressin treatment group and retrospective controls, we expect to have 50 subjects in the intervention group and 150 subjects, assembled from the study sites, in the control group. Assuming a type 1 error of 0.05 and power of 80%, we expect to be able to detect a range of differences in serum creatinine (SCr) depending on the standard deviation of the change (primary endpoint) expected for the groups (see below). Based on results from the REVERSE trial, a change in SCr of as small as 0.05 mg/dL would be able to be detected if the standard deviation for the change approximated 0.10 mg/dL and a pre-specified sample size of 200 subjects, 50 of whom are in the intervention arm, is used for the calculation.

	Δ SCr mg/dL				
Detectable Difference	0.46	0.34	0.23	0.11	0.05
Standard Deviation	1.00	0.75	0.50	0.20	0.10

Given the relatively small number of subjects proposed for inclusion in this terlipressin study, we will likely be underpowered to detect a difference in the other secondary outcomes being explored.

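### Liver transplant by Day 30/90 is compared with controls whose share of transplant-ineligible patients is not fixed, over an undefined at-risk denominator, so a difference in mix alone can bias the result in either direction

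*Combined protocol and SAP*

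**What the plan says.** **Who may enter.** Section 7.3 defines two groups: Group 1, listed or transplant-eligible, and Group 2, ineligible. Criterion 6B reads: "Patients not on the transplant waitlist or transplant eligible are also eligible for the trial (maximum 25 subjects". The synopsis objective words the limit as "Not eligible for liver transplant (limited to 25 patients". Section 7.2 sets the treated group at "Prospective Terlipressin Group - approximately 50 Terlipressin treated subjects".

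**Who the controls are.** Section 7.2 asks for historical patients "that would have met the inclusion/exclusion criteria below as well as having critical clinical data points to enable a comparison" of the two groups. Those criteria include 6B, so ineligible controls are allowed. No quota, matching or stratified sampling sets their share. Neither statement of the cap says whether it covers controls. Section 4 was not updated to match 6B: "The purpose of this open labeled study is to assess safety/efficacy for continuous terlipressin infusion in liver transplant-eligible adult subjects". The synopsis sentence that introduces the criteria likewise names only listed or eligible patients.

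**What is compared.** Sections 5.1 and 13.2 list "Transplant by Day 30 and Day 90 follow up", for the terlipressin group alone and against controls. Section 15.2 computes incidence as new events "divided by the total persons at risk" and applies a two-sided P<0.05 rule. Confounder adjustment is described only for the serum creatinine model in Section 15.1. For ineligible or non-transplanted patients, Section 15.2 adds separate creatinine time points but nothing on transplant, survival or dialysis.

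**The concern.** A patient outside the transplant pathway has little or no chance of a transplant by Day 30 or 90, whatever drug is given. If such patients count in the denominator and their share differs between groups, the crude transplant rates differ even when terlipressin does nothing. The result would then describe how patients were selected rather than what the drug did.

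The way the cap is read matters. Suppose the treated group uses all 25 places. If the cap is trial-wide, no controls are ineligible. If it applies per group, at most 25/150 = 17% of controls are ineligible, against 25/50 = 50% of treated subjects. If it does not bind controls, their share can be anything, including an equal one, but nothing makes it equal. The wording left in Section 4 and the synopsis could also lead sites to abstract only listed or eligible controls.

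Survival and dialysis would blend the same two groups in unknown proportions. An effect there is plausible, but the documents give nothing from which to quantify it.

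**Working it through.** **The plan's own figure.** No power or rate is given for transplant. The only power figure is the creatinine table in Section 15.3, which confirms the sizes to use: "we expect to have 50 subjects in the intervention group and 150 subjects, assembled from the study sites, in the control group". With two-sided 0.05 and 80% power, detectable difference = SD × (1.960 + 0.842) × √(1/50 + 1/150) = 0.4575 × SD. For SD 1.00, 0.75, 0.50, 0.20 and 0.10 this gives 0.458, 0.343, 0.229, 0.091 and 0.046. The plan prints 0.46, 0.34, 0.23, 0.11 and 0.05. Four of the five agree. The SD 0.20 entry does not, but it has no bearing on this point.

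**Inputs from the documents.** 50 treated and 150 controls (15.3); at most 25 ineligible (7.3), taken here as the limit for the treated group; two-sided 0.05 (15.2).

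**Assumptions.** The transplant rate p in eligible patients is the same in both groups (no drug effect) and ranges over 20-50%. Ineligible patients have no transplants. All subjects count in the denominator. There is no dropout. The test is the pooled chi-squared test.

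**Formula.** With m₁ of 50 treated and m₂ of 150 controls eligible, the expected crude rates are p·m₁/50 and p·m₂/150. Their ratio is (m₁/50)/(m₂/150), which does not depend on p. For example, at p = 30%, m₁ = 25 and m₂ = 150, the rates are 0.30 × 25/50 = 15% and 0.30 × 150/150 = 30%, a ratio of 0.50. The probability of P<0.05 is the exact sum over Binomial(m₁, p) and Binomial(m₂, p) counts of all tables with |z| > 1.96.

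| Treated ineligible | Controls ineligible | Rate ratio | p = 20% | 30% | 40% | 50% |
|---|---|---|---|---|---|---|
| 25/50 | 0% | 0.50 | 33.8% | 57.1% | 78.0% | 92.6% |
| 25/50 | 17% (25/150) | 0.60 | 16.8% | 28.2% | 41.8% | 58.0% |
| 25/50 | 25% (38/150) | 0.67 | 10.5% | 15.9% | 23.2% | 32.5% |
| 25/50 | 50% (75/150) | 1.00 | 3.9% | 3.0% | 2.3% | 1.7% |
| 10/50 | 0% | 0.80 | 7.6% | 11.2% | 15.7% | 22.2% |
| 10/50 | 50% (75/150) | 1.60 | 23.0% | 30.6% | 41.9% | 53.4% |

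The fourth row is the equal mix: there is no bias, and the test is conservative. The last row is the reverse imbalance, where the spurious difference is a higher transplant rate on terlipressin.

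**After restriction to eligible patients.** With 25 eligible treated subjects against 75, 125 or 150 eligible controls, the probability of P<0.05 is 4.6-5.6% over the same range of p. The difference detectable with 80% power rises from about 21-23 percentage points (50 versus 150) to about 27-30 (25 versus 150) or up to 32 (25 versus 75).

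**The case against.** A reader might infer that the comparison is already known to be wrong, because half the treated group cannot be transplanted while the controls can. The documents do not support that, for five reasons.

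- Controls must meet the same criteria, including 6B. Their mix is uncontrolled and unknown; it is not known to differ. With equal mixes there is no bias.
- Section 15.2 does not say that ineligible patients stay in the denominator. A transplant-ineligible patient can fairly be read as not at risk of transplant. The defect is that the term is undefined.
- Twenty-five is a maximum, not an expected count. With 10 of 50 ineligible and none among controls, the false-positive rate is 8-22%.
- Criterion 6B describes status at enrolment, and nothing says that it is fixed to Day 90. Zero transplants in that group is an assumption.
- Section 15.2 names no test for this endpoint, the synopsis plans descriptive analysis, and Section 15.3 concedes low power for secondary outcomes.

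The first four stand and set the limits of the point. The fifth stands only in part. Section 15.2 does state a significance rule, a descriptive 15% versus 30% would mislead as readily as a P value, and low power does not protect against bias.

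The point also does not reach every transplant-related endpoint. Creatinine, dialysis and kidney transplant counted after liver transplant concern transplanted patients and are not affected in this way.

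**Conclusion.** The point holds for liver transplant by Day 30 and Day 90. The at-risk denominator is undefined, the eligibility mix of the controls is not fixed, and the comparison is neither stratified nor adjusted by eligibility. Followed as written, it can mistake case mix for a drug effect in either direction.

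With the treated group at the cap, no drug effect and an assumed 20-50% rate in eligible patients, P<0.05 occurs in 34-93% of trials if 0% of controls are ineligible, 17-58% if 17%, 11-33% if 25%, and 2-4% if 50%. These figures rest on the assumed rate, zero transplants in ineligible patients, an all-subjects denominator and a chi-squared test; none of these is stated in the plan. They show what an unequal mix could do and do not predict this trial's result. Any effect on survival and dialysis remains unquantified. Because these are secondary endpoints, this is a change that should be made, and it does not call the primary analysis into question.

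**What to change.** 1. In Sections 13.2 and 15.2, define the at-risk population for transplant by Day 30/90 as Group 1 (listed or eligible) in both arms.
2. Record Group 1 or Group 2 for every retrospective control, from the chart.
3. Report the between-group survival and dialysis comparisons by group and stratified by group.
4. State whether criterion 6B and the cap of 25 apply to controls, and reconcile the synopsis lead-in and Section 4 with Section 7.3.

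A forced group term in the Section 15.1 creatinine model is optional, since that section already screens all potential confounders.

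The cost is some wording and, if the CRF does not already capture it, one chart-derived field. The downside is precision: with fewer patients in the transplant comparison, the detectable difference rises from about 21-23 to about 27-32 percentage points if the treated group reaches the cap.
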